3. OBJECTIVES AND OUTCOMES

Primary objective:

Make a preliminary assessment of the dynamics of subclinical malaria detected by ultrasensitive PCR to guide the design of a matched cohort study of subclinical malaria in Myanmar and along its borders with China and Bangladesh

(The objective of the subsequent matched cohort study, to be reviewed as a separate protocol, will be to compare the incidence of clinical malaria and malaria transmission capacity, in participants with and without subclinical malaria.)

Secondary and exploratory objectives:

1. Within usPCR+ and usPCR- cohorts, test for association between demographic and other risk factors (e.g. occupation, travel) and incidence of clinical malaria and transmission capacity
2. Collect preliminary data to estimate the history of exposure to malaria parasite and mosquito vector species by serological profiling
3. Collect preliminary data to develop a model system to predict future malaria risks using geospatial and satellite data on environmental conditions, patterns of parasite migration and human mobility, field data on vector abundance and malaria burden over time at study sites

Primary outcomes:

1. Proportion of individuals with initially positive usPCR tests that were followed by 1 or more consecutive positive tests on weekly or biweekly testing
2. Proportion of individuals with initially negative usPCR tests that subsequently had at least one usPCR positive test at a second screening 2-4 weeks later.

Primary endpoints:

Not applicable

Secondary and exploratory outcomes:

Infection outcomes and endpoints

1. Incidence of falciparum malaria infection by RDT
2. Incidence of vivax malaria infection by RDT
3. Incidence of mixed falciparum/vivax malaria infection by RDT
4. Incidence of falciparum malaria infection by usPCR
5. Incidence of vivax malaria infection by usPCR
6. Incidence of mixed falciparum/vivax malaria infection by usPCR

Serology endpoint

Seroreactivity to polymorphic malaria/mosquito proteins

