6. STUDY PROCEDURES/EVALUATIONS

6.1. Study Procedures

6.1.1. Screening process

People and locations suspected or known to harbor malaria will be targeted for screening, as described above. As screening progresses, household and workplace contacts of RDT+ and usPCR+ cases will be traced to find more infected individuals until enrollment targets are reached. The sample collection schedule is shown in Table 2.

A very small number of individuals who are found to be RDT+ during the screening process will be asked to provide venous blood, dried blood spots, and travel history. Individuals who are found to be RDT+ during screening, or at any time during the study, will be referred promptly to local health providers for ACT treatment, in compliance with WHO recommendations and NMCP policies, which call for treatment of any RDT+ infection.

Table 2a. Study procedures for population with total 12 weeks of follow up

Procedures	Screening	Follow-up visits in weeks after enrollment				
		4	6	8	10	12
Eligibility/ RDT testing	R					
Informed consent/assent	R					
Enrollment	R					
Contact & demographic Information; hemoglobin testing	R					
Travel history	R	R	R	R	R	R
Dried blood spots (RDT- & usPCR+ at enrollment)	R	R	R	R	R	R
Dried blood spots (RDT- & usPCR- at enrollment)	R	R				
Venous blood collection for RDT+		R; Any time during the study				
Treatment referral for RDT+		S; Any time during the study				

RDT, rapid diagnostic test; usPCR, ultrasensitive PCR; R, research-related procedure; S, standard care procedure

Table 2b. Study procedures for population with total 6 weeks of follow up

Procedures	Screening	Follow-up visits in weeks after enrollment				
		2	3	4	5	6
Eligibility/ RDT testing	R					
Informed consent/assent	R					
Enrollment	R					
Contact & demographic Information; hemoglobin testing	R					
Travel history	R	R	R	R	R	R
Dried blood spots (RDT- & usPCR+ at enrollment)	R	R	R	R	R	R
Dried blood spots (RDT- & usPCR- at enrollment)	R	R				
Venous blood collection for RDT+		R; Any time during the study				
Treatment referral for RDT+		S; Any time during the study				

RDT, rapid diagnostic test; usPCR, ultrasensitive PCR; R, research-related procedure; S, standard care procedure

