6.1.3. Follow-up

All enrolled participants will follow up 2-4 weeks after enrollment. Those who are found to be usPCR negative will provide one additional DBS at a second visit at 2-4 weeks and discharged from the study. Those who are found to be usPCR positive will provide four additional DBS, two weeks apart (weeks 6, 8, 10, and 12), and discharged from the study at Week 12. For the military population who are likely able to provide a total of only 6 weeks follow up, they will return at 2 weeks after enrollment, and the follow up schedule will be weekly.

At each follow up visit, a brief history (including travel history update) will be taken, and dried blood spots will be collected. Those who miss two consecutive follow-up visits will be

discharged from the study. At any time that participants are found to be RDT+, if study personnel qualified to collect venous blood are present, RDT+ participants will provide venous blood for serology and parasite nucleic acid sequencing. Individuals testing RDT+ at any time during the study will be referred for prompt ACT treatment of malaria by local health providers.

Conceptual framework of the study is shown below:

Anticipated duration of screening and enrollment phase: Screening and enrollment will begin at each site after obtaining ethical approval from all relevant administrative and ethical review committees for that site. Because technical capacity for usPCR is not yet established at the China and Bangladesh sites, the study is expected to begin sooner at the Myanmar sites. Screening will be continued until enrollment targets are reached.

Duration of follow-up for each subject: Up to 4 months (~2-4 weeks initial assessment plus up to 1.5-3 months follow-up).

Total study duration: Up to 1.5 years

Retention: We have achieved retention rates of >95% in longitudinal cohort studies in Madaya (unpublished) and Bandarban [54-58] by maintaining strong relationships with the community, including regular community meetings; contributing to community welfare through training health providers and upgrading facilities; and treating informed consent as an ongoing process for the individual and the community [59, 60]. Retention is expected to be lower at sites with refugees and military troops, requiring additional screening at those sites, as noted above.

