7. STATISTICAL CONSIDERATIONS

7.1. Study Outcome Measures

Primary objective:

Make a preliminary assessment of the dynamics of subclinical malaria detected by ultrasensitive PCR to guide study design of a subsequent longitudinal matched cohort study.

(The objective of the subsequent matched cohort study, to be reviewed as a separate protocol, will be to compare the incidence of clinical malaria and malaria transmission capacity, in participants with and without subclinical malaria.)

Secondary and exploratory objectives:

1. Measure the dynamics of subclinical malaria over time and obtain a preliminary estimate of the chronicity of infection over a short period of time
2. Test for association between demographic and other risk factors (e.g. occupation, travel) and incidence of clinical malaria and transmission capacity
3. Collect preliminary data to estimate the history of exposure to malaria parasite and mosquito vector species by serological profiling
4. Collect preliminary data develop a model system to predict future malaria risks using geospatial and satellite data on environmental conditions, patterns of parasite migration and human mobility, field data on vector abundance and malaria burden over time at study sites

Primary outcomes:

1. Proportion of individuals with initially positive usPCR tests that were followed by 1 or more consecutive positive tests on biweekly testing
2. Proportion of screened individuals with negative usPCR tests that subsequently had usPCR positive tests at a second screening test 4 weeks later

Primary endpoints:

Not applicable

Secondary and exploratory outcomes:Infection outcomes and endpoints

1. Incidence of falciparum malaria infection by RDT
2. Incidence of vivax malaria infection by RDT
3. Incidence of mixed falciparum/vivax malaria infection by RDT
4. Incidence of falciparum malaria infection by usPCR
5. Incidence of vivax malaria infection by usPCR

6. Incidence of mixed falciparum/vivax malaria infection by usPCR

Serology endpoint

Seroreactivity to polymorphic malaria/mosquito proteins

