7.4. Analysis Plan

Primary analysis will compare the proportion of individuals with initially positive usPCR tests that were followed by 1 or more consecutive positive tests on biweekly testing. Using the screening results, we will also calculate the proportion of individuals with negative usPCR tests that subsequently had usPCR positive tests at the second screening test.

Secondary analyses will include comparisons based on incidence of species-specific RDT+ and usPCR+, and, for serological studies, breadth (% seropositivity) and magnitude (mean fluorescence intensity) of antibody responses on protein and peptide microarrays.

To understand the dynamics of usPCR positivity, we will construct maximum likelihood models using Markov chains to evaluate risk factors that increase or decrease the probability of going from state to state between monthly sampling time points.

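### Primary outcome 2 is tied to a 4-week retest in Section 7.1, but negatives on the 6-week (military) schedule are retested once, at week 2, and no rule covers unequal intervals

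*Combined protocol and SAP*

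**What the plan says.** The combined protocol and SAP words the two primary outcomes in two ways.

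- **Outcome 2 (initial negatives).** Section 7.1: "Proportion of screened individuals with negative usPCR tests that subsequently had usPCR positive tests at a second screening test 4 weeks later". Section 3: initial negatives "that subsequently had at least one usPCR positive test at a second screening 2-4 weeks later". Sections 2.4.1, 4.1, 6.1.3 and 7.2 also use 2-4 weeks. Section 6.1.1 says about 4 weeks for all usPCR-negative participants and makes no military exception. Section 7.4 gives no interval for the second test.
- **Outcome 1 (initial positives).** Section 3: "1 or more consecutive positive tests on weekly or biweekly testing". Sections 7.1 and 7.4 mention biweekly testing only.
- **Schedules.** Table 2a has visits at weeks 4, 6, 8, 10 and 12. Table 2b, for the population followed for 6 weeks, has visits at weeks 2, 3, 4, 5 and 6. Section 6.1.3 says of the military population that "they will return at 2 weeks after enrollment, and the follow up schedule will be weekly". Each table marks the negatives' blood spot only at screening and the first follow-up visit, which is week 4 in Table 2a and week 2 in Table 2b. Section 6.1.3 discharges negatives after that one retest.
- **Use of the results.** Section 2.4.1 will judge whether a single usPCR result is stable enough to classify infection in the later cohort. For positives it looks at stability over three months; for negatives, at the retest 2-4 weeks later.
- **Model.** Section 7.4 describes Markov transitions between monthly sampling points.

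**The concern.** A proportion that remains positive, or turns positive, by the next test depends on when that test is done. The plan sets the first retest at week 2 for one population and week 4 for the others. Section 7.1 recognises only the week-4 retest for negatives. Section 3 accepts both but does not say whether they are added together, reported apart or adjusted.

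An earlier retest tends to make both positive and negative status look more stable. A military site could then appear to have more stable infections because of its visit calendar alone, and an all-site figure would move slightly the same way. These proportions are meant to inform the choice between single and repeat testing, and the size of the later cohort.

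**Working it through.** **1. The plan's own counts.** Section 7.2 allows up to 1,000 participants per site, of whom it puts 75% as usPCR-negative: 1,000 × 0.75 = 750 per site. Six sites give 6 × 750 = 4,500 negatives, of whom 3,750 are outside the one military site. Observations per person are 1 + 5 = 6 for positives on either schedule and 1 + 1 = 2 for negatives. All agree with Section 7.2. The plan gives no precision calculation for the primary outcomes.

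**2. Who has a value for outcome 2.** Under Section 7.1 read literally, a military negative retested at week 2 and discharged has none: up to 750 of 4,500 (16.7%). Under Section 3 all have a value, at week 2 or week 4.

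**3. Who has a value for outcome 1.** Military weeks 2, 4 and 6 form a two-week series, so outcome 1 is evaluable there even on the biweekly wording. Table 2a opens with a 4-week gap, so it is not strictly biweekly either. What differs is the first retest (week 2 against week 4) and total follow-up (6 against 12 weeks).

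**4. Size for positives (assumed inputs).** Assume exponential residual duration with mean m weeks, a perfect test and no reinfection. Outcome 1 then equals positivity at the first retest, exp(−t/m).

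| Mean m (weeks) | Week 2: exp(−2/m) | Week 4: exp(−4/m) | Gap (points) |
|---|---|---|---|
| 4 | 61% | 37% | 24 |
| 8 | 78% | 61% | 17 |
| 16 | 88% | 78% | 10 |
| 52 | 96% | 93% | 4 |

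With equal numbers of positives per site and one military site of six, at m = 8 the pooled figure is (5 × 60.7 + 77.9)/6 = 63.5%, against 60.7% if everyone were retested at week 4: a shift of about 3 points. At the shared visits the two schedules agree: exp(−4/8) = 61% at week 4 and exp(−6/8) = 47% at week 6.

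**5. Size for negatives (assumed inputs).** At a constant hazard, p(2 weeks) = 1 − √(1 − p(4 weeks)). Pooled = (3,750 × p4 + 750 × p2)/4,500.

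| 4-week conversion | 2-week conversion | Pooled, 1 site of 6 |
|---|---|---|
| 2% | 1.0% | 1.83% |
| 5% | 2.5% | 4.59% |
| 10% | 5.1% | 9.19% |
| 20% | 10.6% | 18.4% |

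The pooled value is about 8% too low in relative terms throughout. Section 5.1 says the study starts in Myanmar, where Figure 3 shows two non-military sites and one military one. With those three sites at equal size, 5% pools to (2 × 5.0 + 2.53)/3 = 4.2%.

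**6. If some conversions are infections missed at baseline.** Suppose half of a 5% conversion is missed infection that does not depend on the interval. The other 2.5% becomes 1 − √0.975 = 1.26% at 2 weeks, so the 2-week figure is 2.5 + 1.26 = 3.76% and the six-site pooled value is (3,750 × 5.0 + 750 × 3.76)/4,500 = 4.79%. If all of it is missed infection, the interval effect vanishes.

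**7. The Markov model.** Intervals from enrolment are 4, 2, 2, 2, 2 weeks in Table 2a and 2, 1, 1, 1, 1 in Table 2b. A common monthly step describes neither.

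**The case against.** The strongest reply is that most of the text already accommodates both schedules. Section 3 does, and Section 7.2, within the statistical chapter itself, calls 2-4 weeks sufficient for negatives. The shorter military follow-up is stated openly, and Section 2.3 calls the study largely descriptive. On that view Section 7.1 carries a narrower wording and nobody intends to discard the military negatives. This largely stands: their loss is a risk of literal reading, not a planned result. It does not answer how 2-week and 4-week retests are to be combined.

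A reader might infer three stronger things that the documents do not support.

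- **That military positives have no valid outcome 1 because they are tested weekly.** Their week 2, 4 and 6 samples supply a two-week series.
- **That the plan commits to raw pooling.** Section 7.4 does not say so, and the all-sites phrase in Section 7.2 concerns the later cohort. The plan is silent.
- **That negatives on the 6-week schedule can never have a 4-week retest.** Section 6.1.1 read alone gives every negative one at about 4 weeks. It conflicts with Table 2b and Section 6.1.3, and the passages must be reconciled.

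It is also fair that a perfect-test model sets aside the question Section 2.4.1 asks, namely whether one result classifies correctly. Section 2.2.2 says the duration of low-density infections has not been described, so no single mean can be defended.

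**Conclusion.** The definitions of outcome 2 conflict in the current text, and the plan lacks a rule for unequal retest intervals. Following it as written either drops up to 750 negatives or counts 2-week and 4-week conversions in the same primary proportion. For outcome 1 the point is narrower: it is evaluable on both schedules, but at different first-retest times, and stability over three months cannot be observed in anyone followed for 6 weeks.

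The effect is potentially large between schedules and modest in an all-site figure. These sizes rest on constant hazards, a perfect test, equal site sizes and full enrolment. They shrink with long-lasting infections, or where conversions mainly reflect detection near the assay limit. One might infer that the artefact would overturn the decision in Section 2.4.1. That section asks only whether most results stay the same, and a pooled shift of this size is unlikely by itself to change the answer. The greater risk is a difference between sites read as biology. The point deserves correction; it does not threaten the usability of the data.

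**What to change.** - Reconcile Sections 3, 6.1.1, 7.1 and 7.4 and Tables 2a and 2b to one definition of each primary outcome that fits both schedules.
- Report outcomes 1 and 2 separately by schedule, using the actual retest interval, and not as one raw pooled proportion.
- Keep outcome 1 as defined. For comparing positives across sites, add positivity at weeks 4 and 6, the visits both tables share, as a supplementary figure.
- Fit the Markov model with actual sampling intervals in place of a monthly step.
- State that the three-month stability conclusion applies to the 12-week population only.

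The cost is redrafting and a small change to the model specification, with no added visits or samples. The downside is smaller groups behind each reported proportion and no three-month conclusion for the military population. Expressing conversions per person-week is not needed, and would create its own schedule artefact if many conversions are infections missed at baseline.

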7.2. Sample Size Considerations

This preliminary study is designed for better understanding of the dynamics and stability of usPCR status. The preliminary data are needed to estimate the required sample size for the subsequent matched cohort study, by assuming a McNemar test at $\alpha=0.05$, two-sided, on the observed proportions of usPCR+ and usPCR- participants who develop a positive RDT in 5 years of follow-up for all sites combined. The results of this preliminary study as well as data from other recent and ongoing surveillance and studies will allow us to estimate the average annual probability of a positive RDT. We will then be able to calculate the sample size to obtain adequate statistical power to reject the null hypothesis that the true risks in usPCR+ and usPCR- individuals are equal if the true relative risk of the estimated 5-year probability of a positive RD.

The sample size of this preliminary study (up to 1,000 per site) is planned within logistical and financial constraints. A total of 250 usPCR+ is conservatively estimated. Observing usPCR+ for 6 or 12 weeks (total number of observation = 6) is feasible, and will provide a meaningful preliminary estimate of the stability and dynamics of usPCR+ infections. For every 100 enrollees, we estimate that at least 75% will be usPCR-. Observation of usPCR-individuals (sample size may be as many as 750 per site) for 2-4 weeks (total number of observation = 2) will also be sufficient and meaningful to judge the stability of usPCR- status.

7.3. Participant Enrollment and Follow-Up

Recruitment will begin in the 2018 May-October rainy season and continue until enrollment targets are reached. The duration of follow-up for each subject will be up to 12 weeks. The total study duration will be up to 1 year. At each site, enrollment will be paced such that at least 100 participants are enrolled in both the rainy and in the dry season, permitting us to assess seasonal variation in prevalence of infection.

7.4. Analysis Plan

Primary analysis will compare the proportion of individuals with initially positive usPCR tests that were followed by 1 or more consecutive positive tests on biweekly testing. Using the screening results, we will also calculate the proportion of individuals with negative usPCR tests that subsequently had usPCR positive tests at the second screening test.

Secondary analyses will include comparisons based on incidence of species-specific RDT+ and usPCR+, and, for serological studies, breadth (% seropositivity) and magnitude (mean fluorescence intensity) of antibody responses on protein and peptide microarrays.

To understand the dynamics of usPCR positivity, we will construct maximum likelihood models using Markov chains to evaluate risk factors that increase or decrease the probability of going from state to state between monthly sampling time points.

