2.4.1. Preliminary study

In this study, a small number of asymptomatic infections detected by ultrasensitive PCR (usPCR) will be followed and tested intensively for three months to measure the temporal dynamics of these infections. A much larger number of uninfected individuals will be followed

for just 2-4 weeks (two visits), providing a comparator group for the infected cohort. The validity of our results in a subsequent matched cohort study depends, in part, on our ability to accurately classify infection status using a single usPCR result. In other words, do we have sufficient confidence in the correct classification of malaria infection positive and negative status using usPCR test at the beginning of the study? While there is no gold standard test more sensitive than usPCR, repeated usPCR testing offers a surrogate. Presumably, in a low transmission setting, someone who is truly uninfected on the first testing should remain negative on multiple consecutive tests, but this remains to be confirmed.

If this initial evaluation confirms that usPCR results are relatively stable - i.e., that most usPCR+ infections remain positive on most or all repeated testing over the course of three months, and that most usPCR- infections remain negative upon re-testing 2-4 weeks later, then we can move forward with the cohort study with confidence that our initial classification of exposure is a meaningful basis for assessing subsequent outcomes. If, however, a single usPCR result is found to be "unstable", we may need to consider testing at least twice before assigning infection status. Similarly, we may wish to increase the sample size if we determine that the sensitivity and specificity of a single usPCR test (compared to results of multiple testing) is high enough to proceed with single testing at screening and enrollment, but lower than ideal (e.g. sensitivity/specificity 50-75%).

2.4.2. Design of the subsequent matched cohort study (to be submitted for ethical review later as a separate protocol)

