4. STUDY DESIGN

4.1. Overview

- Prospective, multi-site short longitudinal study
- Up to six study sites, each with >2 villages, towns, unions, refugee camps or plantations, or a single military base. Alternative and additional sites may be added to ensure enough infected cases.
- Screening for eligibility (age at least 0.5 year; able & willing to strictly follow study protocol and to provide written informed consent or assent as appropriate)
- Enroll and consent eligible individuals
- RDT-positive: one-time enrollment for data and venous blood collection; Refer to and ensure appropriate treatment by care providing team; No study-related follow up
- RDT-negative: Collect data and DBS samples; Return to research clinic in 2-4 weeks
- PCR-negative participants: One follow up visit approximately 2-4 weeks after enrollment
- PCR-positive participants: Five follow up visits at approximately 4, 6, 8, 10, and 12 weeks (for those with total 12 weeks follow up) or 2, 3, 4, 5 and 6 weeks (for those with total 6 weeks follow up) after enrollment
- Total up to 6000 residents in up to six study site of all ages in villages, refugee camps, military bases, and work sites are to be enrolled
- Finger stick blood sampling will be done for RDT and dried blood spot sampling in all participants at each scheduled and unscheduled visit.
- Venous sampling will be done for participants with RDT+ infections detected at times when study staff trained for venous sampling are present. Blood volumes at any time point are limited to 2 mL for children aged < 3 years, 3 mL for age 3-5 years, and 5 mL for older children and adults.
- Estimated duration of study: 18 months

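### Section 7.4 does not say how usPCR error enters its Markov model, so transitions between observed results could be misread as infection clearance or duration

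*Combined protocol and SAP*

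**What the plan says.** Section 7.4 gives the model one sentence. Its aim is "To understand the dynamics of usPCR positivity", and its method is "maximum likelihood models using Markov chains to evaluate risk factors that increase or decrease the probability of going from state to state", with steps taken "between monthly sampling time points". It mentions no hidden infection state, no sensitivity or specificity parameter, and no sensitivity analysis for test error.

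Three other places bear on this:

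- **Section 2.4.1** leaves single-test accuracy open. It says: "While there is no gold standard test more sensitive than usPCR, repeated usPCR testing offers a surrogate". It plans for the case where accuracy is good enough to proceed "but lower than ideal (e.g. sensitivity/specificity 50-75" per cent). Its responses, testing twice or enlarging the sample, concern the later cohort.
- **Section 7.1** lists as a secondary objective to "obtain a preliminary estimate of the chronicity of infection over a short period of time". Section 7.4 names no other method that would deliver this.
- **Section 4.1** sets the visits: "PCR-positive participants: Five follow up visits at approximately 4, 6, 8, 10, and 12 weeks", or weeks 2, 3, 4, 5 and 6 on the shorter schedule. Participants negative at enrolment have one follow-up visit at 2-4 weeks. Only the first gap of the 12-week schedule, or a 4-week return visit by a usPCR-negative participant, is close to a month.

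**The concern.** In a chain fitted to observed results, a missed detection of a continuing infection counts as a loss, and the next positive counts as a gain. Losses are inflated and time spent positive looks short. Covariates are exposed too. If age, site or occupation goes with parasite density or laboratory performance, it changes the miss rate, and the model shows this as an effect on transition.

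Uneven detection is plausible from the documents. Infections may lie near the assay's detection limit (2.2.1). Assays run in several regional laboratories (6.2.1), and capacity was not yet established in Bangladesh and China (5.1).

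At stake are the answer to the chronicity objective and the interpretation of any risk factor the model identifies.

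**Working it through.** **The plan's own figures.** Section 7.2: 1,000 per site × 0.75 = 750 usPCR-negative; 1 + 5 = 6 observations for usPCR-positive participants; 1 + 1 = 2 for negative ones. All reproduce. The 250 usPCR-positive participants are called a total but equal 25% of one site of 1,000; 25% of 6,000 would be 1,500. The smaller figure is used here. The plan gives no precision or duration figure for the Markov model.

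**Assumptions not in the documents.** True mean duration D of 8, 13 or 26 weeks (exponential); prevalence 0.05 or 0.25; specificity 1 or 0.99; errors independent between visits given infection status, except in step 5. Sensitivity (Se) is varied. Tests are at 0.05 two-sided, which section 7.2 states only for the later cohort.

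**Step 1: by hand.** With specificity 1 and no new infection, the chance that a positive is followed by a negative t weeks later is 1 − Se·exp(−t/D). For Se 0.75, D 26 and t 2 this is 1 − 0.75 × 0.926 = 0.31. The true loss is 1 − 0.926 = 0.07.

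As a rate, apparent loss = 1/D + (−ln Se)/t. With 1/26 = 0.0385 and −ln 0.75 = 0.2877:

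| Gap t | Apparent rate per week | Apparent mean |
|---|---|---|
| 4 weeks | 0.0385 + 0.0719 = 0.1104 | 9.1 weeks |
| 2 weeks | 0.0385 + 0.1438 = 0.1823 | 5.5 weeks |
| 1 week | 0.0385 + 0.2877 = 0.3262 | 3.1 weeks |

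The error term is divided by t, so closer visits make the same infection look shorter.

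**Step 2: full observed-state fit.** A two-state continuous-time chain was fitted by maximum likelihood to the exact expected transition counts on the actual intervals. The table gives the fitted mean as a share of the true mean, with its range over the assumptions above:

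| Se | 12-week schedule | 6-week schedule |
|---|---|---|
| 0.95 | 48-86% | 32-74% |
| 0.75 | 20-52% | 11-34% |
| 0.50 | 9-31% | 5-18% |

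With Se and specificity both 1 the share is 100%, as it should be. For a true 13 weeks, prevalence 0.25, Se 0.75 and specificity 0.99, the fit gives 4.5 weeks on the 12-week schedule and 2.7 on the 6-week one. Section 6.1.3 gives the shorter schedule to the military population, and occupation is a named risk factor (section 3). Visit spacing alone could therefore look like a difference in clearance.

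**Step 3: a factor that changes detection only.** By the step 1 formula at t = 2 and D = 26, Se 0.80 against 0.90 gives (0.0385 + 0.1116)/(0.0385 + 0.0527) = 1.65, though true clearance is identical. Simulation used 250 positive and 750 negative participants, the 12-week schedule, prevalence 0.25, specificity 0.99 and 300 replicates:

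| Se by group | Apparent clearance ratio (D 13; D 26) | Rejected |
|---|---|---|
| 0.95 v 0.75 | 2.18; 2.85 | 100%; 100% |
| 0.75 v 0.50 | 2.03; 2.30 | 100%; 100% |
| 0.90 v 0.80 | 1.43; 1.66 | 75%; 94% |
| 0.75 v 0.75 | 1.00; 1.01 | 4%; 10% |

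**Step 4: hidden Markov model, errors independent.** Same design, Se estimated by group, specificity fixed at its true 0.99, 60 replicates. The true-null clearance effect was rejected in 5% of replicates in each case:

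| Se by group | True mean (weeks) | Estimated mean (weeks) | Clearance ratio |
|---|---|---|---|
| 0.95 v 0.75 | 13 | 12.6 | 0.96 |
| 0.75 v 0.50 | 13 | 13.7 | 1.09 |
| 0.90 v 0.80 | 26 | 25.4 | 0.99 |

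**Step 5: hidden Markov model, errors correlated.** Here density moves in and out of detectability with an assumed 3-week relaxation time. It is detectable 75% against 60% of the time, with a true mean of 26 weeks, specificity 1 and 125 v 125 participants. In two separate runs, the hidden model that assumes independent errors gave 18.6 and about 20 weeks on the 12-week schedule, and 12.7 and about 15 on the 6-week one. It rejected a true null in 20-22% and 27-28% of studies respectively. The observed-state fit gave 9.1 and 8.4 weeks on the two schedules and rejected in 58% and 48%.

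**The case against.** The strongest reply is that the model's target is test status. Section 7.4 speaks of usPCR positivity, section 7.2 of the stability of usPCR status, and section 2.4.1 asks whether one result can classify exposure in the later cohort. For that question, observed transitions with detection dropouts included are the quantity wanted, and a covariate that makes status unstable is informative. This stands, and it is why the observed-state chain should be kept. It does not cover the chronicity objective, which concerns infection.

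A reader might infer that the plan declares usPCR results error-free. It does not: section 7.4 is silent, and a maximum-likelihood Markov model can carry a hidden state.

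A reader might also take 50-75% as the expected accuracy. Section 2.4.1 offers it as an example contingency, judged against repeated testing, and section 2.2.1 describes the assay as reliable at very low densities. The size of the bias therefore rests on an unknown.

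Finally, the hidden model can be oversold. Its good results in step 4 come from data that meet its own assumptions. Step 5 shows it is better than the naive fit but not a cure.

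**Conclusion.** The point holds as an omission with a practical consequence. If the chain is fitted to observed results and read as infection, mean duration on the 12-week schedule comes out at about 48-86% of the truth at sensitivity 0.95 and 20-52% at 0.75, and lower on the 6-week schedule. These shares rest on the assumed durations, prevalences and specificities and on errors independent between visits. Correlated errors would reduce the bias.

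Two stronger conclusions are not supported. The first is that false risk factors are near certain. The effect in step 3 needs a covariate that really shifts sensitivity, and no document gives such a shift for age, site or occupation; with equal sensitivity on one schedule there is little or no false effect. The second is that the follow-on cohort's matching would be misdirected. Section 2.4.2 bases matching on covariates known or suspected to be associated with malaria risk, not on this model's output.

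The study is largely descriptive, and its primary proportions are not affected by this change. The amendment is still worth making, because test error is an uncertainty the study was set up to examine.

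**What to change.** In section 7.4:

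1. Keep the observed-state chain, labelled as describing the stability of usPCR status.
2. Add a hidden (misclassification) Markov model as the basis for any statement about infection duration, clearance or acquisition.
3. Use the actual visit intervals in both models in place of monthly steps.
4. Let each risk factor act on sensitivity as well as on transition.
5. Estimate sensitivity from the six observations per usPCR-positive participant, and vary specificity over a short range, for example 0.98-1.00.
6. Add a sensitivity analysis for errors correlated between visits.

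This needs SAP wording and some extra analysis, but no new visits, samples or participants. The costs are wider intervals and results that depend on the error assumptions. Under correlated detectability some bias remains, particularly on the 6-week schedule, and the report should say so.
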